2.4 Study Objectives

2.4.1 Purpose

The purpose of this study will be to prospectively evaluate the outcomes of patients with hepatocellular carcinoma (HCC) who undergo DEB-TACE with the Surefire Precision Infusion System for intentional effect of down-staging patients to OLT.

Patients with HCC and who are being evaluated for liver transplantation but outside Milan criteria and meet the eligibility criteria will be enrolled in the prospective single arm study.

Results of the prospective cohort will be compared to matched historical control patients who were previously treated with DEB-TACE, delivered with standard endhole catheters. This includes all patients treated at the University of Colorado since 2009 treated with 100-300 micron beads for whom follow-up is available.¹ The data are as follows.

	1-Month Response						
	[name] Criteria				Vesselle, G., et al. (2015) Range Criteria		
	0-3 cm	3-7 cm	>7 cm	Total	<5 cm	>=5 cm	Total
Count	84	60	8	152	129	23	152
Range	1.3-3.0 cm	3.2-7.0 cm	7.6-17.0 cm	1.3-17.0 cm	1.3-4.8 cm	5.0-17.0 cm	1.3-17.0 cm
Number Complete Response	33	15	0	48	47	1	48
Percentage Complete Response	39.29%	25.00%	0.00%	31.58%	36.43%	4.35%	31.58%
Number Partial Response	32	39	6	77	58	19	77
Percentage Partial Response	38.10%	65.00%	75.00%	50.66%	44.96%	82.61%	50.66%
Number Stable Disease	14	4	1	19	17	2	19
Percentage Stable Disease	16.67%	6.67%	12.50%	12.50%	13.18%	8.70%	12.50%
Number Progressive Disease	5	1	1	7	6	1	7
Percentage Progressive Disease	5.95%	1.67%	12.50%	4.61%	4.65%	4.35%	4.61%
Number Lost To Follow-up*	0	1	0	1	1	0	1
Percentage Lost To Follow-up*	0.00%	1.67%	0.00%	0.66%	0.78%	0.00%	0.66%
Total	84	60	8	152	129	23	152

¹ We have robust follow-up on these patients, which is the main reason that we are intending to use this historical comparator.

	6-Month Recurrence (Complete & Partial Response)						
	[name] Criteria				Vesselle, G., et al. (2015) Range Criteria		
	0-3 cm	3-7 cm	>7 cm	Total	<5 cm	>=5 cm	Total
Patients with Complete Response at 1-month	33	15	0	48	47	1	48
Number Lost To Follow-up at 6-months	2	3	0	5	5	0	5
Percentage Lost To Follow-up at 6-months	6.06%	20.00%		10.42%	10.64%	0.00%	10.42%
Number No Recurrence at 6-months	19	4	0	23	23	0	23
Percentage No Recurrence at 6-months	57.58%	26.67%		47.92%	48.94%	0.00%	47.92%
Number Recurrent Disease at 6-months	12	8	0	20	19	1	20
Percentage Recurrent Disease at 6-months	36.36%	53.33%		41.67%	40.43%	100.00%	41.67%
Subtotal	33	15	0	48	47	1	48
Patients with Partial Response at 1-month	32	39	6	77	58	19	77
Number Transplanted	5	3	0	8	7	1	8
Percentage Transplanted	15.63%	7.69%	0.00%	10.39%	12.07%	5.26%	10.39%
Number Continue TACE to Complete Response	4	0	0	4	4	0	4
Percentage Continue TACE to Complete Response	12.50%	0.00%	0.00%	5.19%	6.90%	0.00%	5.19%
Number Continue TACE to Partial Response	6	12	4	22	15	7	22
Percentage Continue TACE to Partial Response	18.75%	30.77%	66.67%	28.57%	25.86%	36.84%	28.57%
Number Continue TACE to Stable Disease	1	5	0	6	2	4	6
Percentage Continue TACE to Stable Disease	3.13%	12.82%	0.00%	7.79%	3.45%	21.05%	7.79%
Number Continue to Progressive Disease	12	10	0	22	21	1	22
Percentage Continue to Progressive Disease	37.50%	25.64%	0.00%	28.57%	36.21%	5.26%	28.57%
Number Continue TACE unknown status	3	3	0	6	5	1	6
Percentage Continue TACE unknown status	9.38%	7.69%	0.00%	7.79%	8.62%	5.26%	7.79%
Number Change Tx	1	4	2	7	2	5	7
Percentage Change Tx	3.13%	10.26%	33.33%	9.09%	3.45%	26.32%	9.09%
Number Deceased by 6-months	0	2	0	2	2	0	2
Percentage Deceased by 6-months	0.00%	5.13%	0.00%	2.60%	3.45%	0.00%	2.60%
Subtotal	32	39	6	77	58	19	77

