3. STUDY DESIGN

3.1 Study Design

This is a single institution prospective clinical trial with historical matched controls.²

This protocol standardizes DEB-TACE delivery with the Surefire Precision Infusion System.

This protocol does not change patient therapy as the Surefire Precision Infusion System is a standard of care device. All patient safety monitoring, treatment procedures and follow-up procedures will be performed in accordance with standard clinical practice.

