3.3 Sample Size

Fifty (50) subjects will be enrolled in the prospective arm.

Data from one hundred (100) historical randomly sampled control subjects (1:2 ratio) will be selected.

The statistical basis for the sample size is provided in Section 4.3.

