3.5.2 Inclusion Criteria

1. Patients aged 18 years or older with the diagnosis of HCC currently being evaluated for liver transplantation and considered for downstaging.
2. Patients undergoing Surefire DEB-TACE procedure as clinically determined to be part of their standard of care treatment plan.

² In order to test the hypothesis (section 2.4), this prospective study has been designed for eligible participants to receive DEB-TACE with the Surefire Precision Infusion System. Historical matched patients, who previously underwent the DEB-TACE using a standard endhole catheter, will serve as the control group for this study (section 3.1). Given the lack of available comparator data, it is most appropriate to gather the data single arm and with the data develop an appropriate statistical framework for comparison.

3. Meets Milan criteria: a single tumor that is < 5cm or a maximum of 3 tumors with each tumor <3cm AND/OR meets UCSF criteria: a single tumor that is < 6.5 cm in diameter or 2 lesions < 4.5cm with total tumor diameter <8 cm AND/OR is outside of both Milan and UCSF criteria and is being evaluated for downstaging.
4. No portal invasion or extrahepatic spread.
5. No previous chemotherapy, radiotherapy or transarterial embolization (with or without chemotherapy).
6. Eastern Cooperative Oncology Group (ECOG) performance status of 0 or 1.
7. Preserved liver function (Child-Pugh Class A or B).

3.5.3 Exclusion Criteria:

1. Advanced bilirubin levels > 3 mg/dl
2. INR > 2 in the absence of anticoagulation therapy
3. AST or ALT>5 upper limit of normal or >250 U/l
4. Advanced tumoral disease, defined as vascular invasion, extrahepatic spread, or diffuse HCC (50% liver involvement)
5. Contraindications for doxorubicin administration.
6. Child's Class C

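### The historical controls are called matched, but no matching variable is named and the eligibility criteria are not applied to them, so differences in case mix can pass for a catheter effect

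*Combined protocol and SAP*

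**What the plan says.** **Who the controls are.** Section 2.4.1 states that "Results of the prospective cohort will be compared to matched historical control patients who were previously treated with DEB-TACE" through standard end-hole catheters. It then sets the pool: "This includes all patients treated at the University of Colorado since 2009 treated with 100-300 micron beads for whom follow-up is available". The response table that follows counts 152. Section 3.3 gives the selection rule: "Data from one hundred (100) historical randomly sampled control subjects (1:2 ratio) will be selected".

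**What they are called.** Section 3.1 reads "This is a single institution prospective clinical trial with historical matched controls". The hypothesis in 2.4.2 and footnote 2 also use the word matched. None of these places names a matching variable, a tolerance or a method.

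**Who the Surefire patients are.** Section 2.4.1 says that patients "being evaluated for liver transplantation but outside Milan criteria and meet the eligibility criteria will be enrolled in the prospective single arm study". Criterion 1 of 3.5.2 is "Patients aged 18 years or older with the diagnosis of HCC currently being evaluated for liver transplantation and considered for downstaging". Sections 3.5.2 and 3.5.3 also require no earlier chemotherapy, radiotherapy or embolization, ECOG 0 or 1, Child-Pugh A or B, no portal invasion or extrahepatic spread, and limits on bilirubin, INR and AST/ALT. Criterion 3 admits tumours within Milan, within UCSF or outside both.

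**How the groups are compared.** Under 4.4, local recurrence rate (LRR) is compared by an unadjusted Fisher exact test. Change in enhancing tumour size is modelled on catheter, age and sex. The Cox models for time to progression and survival add a stage/severity variable that is not defined. Baseline characteristics are tested between groups, but nothing follows from an imbalance.

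**The concern.** The hypothesis in 2.4.2 is wholly a contrast between catheters in transplant candidates treated for downstaging. The Surefire side of that contrast passes a list of criteria. The control side, as written, passes three filters: end-hole catheter, bead size and available follow-up. A random draw from such a pool reproduces the pool's case mix; it does not match anyone to the Surefire patients.

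Prior treatment, liver function, transplant candidacy and tumour size can all plausibly affect response and recurrence. If they differ between the groups, the difference is counted as a catheter effect, and neither the Fisher test nor the age and sex model can separate the two. The bias could run either way: sicker or previously treated controls would flatter Surefire, while a pool of mostly small tumours would work against it. Section 4.3 intends these data to size a multicenter trial, so the error would carry forward.

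**Working it through.** **1. The plan's own power figure.** Section 4.3 gives 0.78 for LRR 30% versus 10%, alpha 0.05 (taken as two-sided), with 100 controls and 50 Surefire patients. The continuity-corrected arcsine approximation to Fisher's test is

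power = Φ( √(4·n1·n2/(n1+n2)) × [asin√(p1 − 1/(2·n1)) − asin√(p2 + 1/(2·n2))] − 1.96 )

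With the numbers in: √(4·100·50/150) = 11.547; asin√0.295 − asin√0.11 = 0.574 − 0.338 = 0.236; power = Φ(2.73 − 1.96) = 0.78. The stated figure is reproduced. Full enumeration with the usual two-sided Fisher p-value gives 0.81, and step 5 uses that version.

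**2. Criteria set side by side.**

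| Requirement | Surefire (3.5.2, 3.5.3) | Controls (2.4.1, 3.3) |
|---|---|---|
| In transplant evaluation, considered for downstaging | yes | not stated |
| No earlier chemotherapy, radiotherapy or embolization | yes | not stated |
| ECOG 0–1, Child-Pugh A/B, laboratory limits | yes | not stated |
| No portal invasion or extrahepatic spread | yes | not stated |
| Tumour size | hardly restricted (criterion 3) | not restricted |
| Bead size 100–300 micron | not stated | yes |
| Follow-up available | not a condition | yes |

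The documents do not give the number of the 152 that fail any of these rows, so the effect of the eligibility gap itself cannot be computed.

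**3. Sensitivity to one case-mix variable, tumour size.** This is an illustration only. Inputs from the 2.4.1 table: 1-month complete response (CR) is 47/129 = 36.4% below 5 cm, 1/23 = 4.3% at 5 cm or more, and 48/152 = 31.6% overall; 23/152 = 15.1% are 5 cm or more. Let f be the Surefire share at 5 cm or more (assumed) and suppose the catheters are identical:

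expected Surefire CR = (1 − f) × 47/129 + f × 1/23

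For f = 0.5 this is 0.5 × 0.364 + 0.5 × 0.043 = 0.204. The last column is the exact two-sided Fisher rejection probability for 100 versus 50, with controls at 31.6%.

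| f | Expected Surefire CR | Chance of a false significant result |
|---|---|---|
| 0% | 36.4% | 8% (nearly all favouring Surefire) |
| 15.1% (pool mix) | 31.6% | 4% |
| 30% | 26.8% | 7% (nearly all against Surefire) |
| 50% | 20.4% | 27% (against Surefire) |
| 75% | 12.4% | 74% (against Surefire) |

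**4. Masking, same set-up.** If Surefire truly added 20 points of CR in each size stratum, the chance of a significant benefit would be 62% at the pool mix, 41% at f = 30%, 17% at 50% and 3% at 75%.

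**5. Price of fewer controls.** Exact two-sided Fisher power for 30% versus 10% with 50 Surefire patients:

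| Eligible controls | Power |
|---|---|
| 100 | 0.81 |
| 75 | 0.76 |
| 50 | 0.64 |
| 23 | 0.51 |

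Keeping 100 requires 100/152 = 66% of the pool to be eligible. The 23 is the number with tumours of 5 cm or more and serves as a low case.

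**The case against.** The plan does say matched, in four places, and a sponsor could answer that screening and matching were intended and simply not written down. That is fair as to intent, but no variable or method is given and 3.3 prescribes random sampling, so the text cannot be followed as matching.

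A reader might infer that ineligible patients are in the control group. The documents do not support that. They are silent; nothing shows that any control had prior therapy, vascular invasion or Child-Pugh C disease. The defect is that nothing excludes them.

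A reader might also take 27% or 74% as the error rate of a planned analysis. It is not. The plan specifies no Fisher test on 1-month CR; Fisher's test is for LRR, and tumour response is analysed as a continuous change. Nor does the 5 cm contrast carry over to LRR: section 3.11 drops patients with residual disease at one month from the six-month recurrence evaluation, and 47 of the 48 control complete responders were below 5 cm. The size shares are assumptions, the upper stratum rests on 23, and at 15% to 30% the false-positive rate stays near nominal.

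Finally, size is not what eligibility screening would fix. Criterion 3 admits nearly any size, so the imbalance illustrated above would largely survive screening alone. This objection stands, and it is why the remedy needs a second part.

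The plan also has partial mitigations: baseline comparisons, a stage/severity term in the Cox models, pilot status, and footnote 2, which leaves the comparison framework to be developed. They soften the point but do not reach LRR or the change in enhancing size.

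**Conclusion.** The concern holds in this form: the matching is undefined and at odds with the random draw, the eligibility criteria are not applied to controls, and the two main comparisons do not adjust for tumour size, stage or liver function. This should be fixed before any between-catheter result is reported or used to size a later trial.

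The size of the bias from unscreened controls is unknown, because the documents do not give the share failing each criterion. The size illustration shows only that the outcome is sensitive to case mix: a false-positive rate from 4% to 74% over Surefire shares of 15% to 75%. It assumes that the table's size-specific rates hold for both groups and that its counts are patients.

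The direction is also open. A reader might infer that the plan is biased against Surefire, because 84 of 152 controls have tumours of 3 cm or less while sections 1.2 and 2.4.1 describe patients outside Milan. Criterion 3 also admits patients within Milan, so the documents do not settle it.

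**What to change.** 1. In 2.4.1 and 3.3, restrict controls to patients who met every criterion of 3.5.2 and 3.5.3 at their first DEB-TACE, reading criterion 2 as end-hole. Screen from charts without reference to outcome, and report the number failing each criterion.
2. Use all eligible controls instead of a random 100, and replace the random draw with matching or adjustment on baseline tumour size. For LRR this means a size-stratified or size-adjusted comparison in place of the crude Fisher test; for change in enhancing size, add baseline size to age and sex. Define the stage/severity variable in the Cox models.
3. State one index-procedure rule for the 1-month and 6-month assessments and apply it to both groups. Section 3.11 counts 1-month response from retreatment for retreated study patients; anchoring controls at their first procedure without reconciling this would create a new asymmetry.
4. Reconcile the outside-Milan population in 1.2 and 2.4.1 with criterion 3.
5. Restate the 4.3 power table for the number of controls left.

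**Cost.** Chart review of at most 152 patients at the same hospital, plus wording changes. The real price is precision, as in step 5 of the working, and it could be substantial if the criteria are read as outside Milan only. Study data entry stopped on 18 June 2018, so the sponsor would have to provide for the control review separately.

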2.2 Study Device

2.2.1 Device Description

The Surefire® Precision Infusion System (Surefire Medical, Inc., Westminster, CO) is a 0.021" lumen coaxial microcatheter with the Surefire Expandable Tip at the distal end. It has an outer sheath to facilitate expanding and collapsing the Surefire Expandable Tip. The Surefire Precision serves as the conduit for physician-specified agents such as contrast agents, flush solutions, and embolic beads. It is compatible with standard 0.018" guide wires, infusion syringes, rotating hemostatic valves (RHVs/Tuohy Borsts), and embolic hydrogel particles 500 μ m or less in size and glass microspheres 110 μ m or less in size. The soft, pliable, funnel-shaped Surefire Expandable Tip is sized for use in vessels of 1.5mm to 3.5 mm.

[figure not shown]
The Surefire tip can be expanded or collapsed re-positioning during an interventional procedure by simply retracting or advancing the inner microcatheter while holding the outer sheath stationary. The Surefire expandable tip collapses during forward flow, and then dynamically seals off the vessel with reversal of flow, analogous to a valve. The Surefire expandable tip is designed to improve infusion efficiency of compatible embolic agents while maintaining antegrade flow in the vessels.

The expandable tip of the Surefire Infusions System has been clinically demonstrated to cause a slight decrease in intra-arterial pressure in the antegrade or downstream vascular compartment (15, 16). Although this device was designed primarily to prevent retrograde reflux of embolic agents, it also enables improved penetration of embolic spheres into the target tissue.

Furthermore, by eliminating reflux, this catheter enables the ability to control the dosimetry, so now the dose can be tailored to the tumor size and not depend upon the flow dynamics of the tumor.

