3.8 Treatment Procedures

No more patients will undergo treatment procedures as of 06/18/2018.

All patients enrolled in this protocol will receive DEB-TACE, which is the standard of care prescribed by their physician.

Lactate whole blood venous will be collected prior to procedure.

Standard 5 Fr and 3 Fr catheters will be used to perform diagnostic angiography to map the hepatic vasculature to the tumor. Using standard technique, the target vessel feeding the tumor will be catheterized and DEB-TACE administered using the Surefire Precision catheter.

The Doxorubicin dosing used in the DEB-TACE will be based upon tumor volume as follows:

Doxorubicin Dosimetry by Tumor Volume		
Tumor Diameter (cm)	Tumor Volume (cc)	Doxorubicin (mg)
3	14.14	75
4	33.51	75
5	65.45	100
6	113.10	150
7	179.59	150
8	268.08	150

DEB-TACE will be administered until the first of the following endpoints is reached:

- Achievement of target dose with stasis
- Leeching of contrast through the expandable tip
- Development of distal intrahepatic collaterals

Note: In hypervascular tumors, the additional use of bland spheres may be needed to achieve the DEB-TACE delivery endpoint.

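### Bead size is a selection condition for the historical controls but is not set for Surefire patients, so embolic type may be confounded with catheter type

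*Combined protocol and SAP*

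**What the plan says.** - **Controls.** Section 2.4.1 defines the comparator pool as endhole DEB-TACE patients at the same institution since 2009, "treated with 100-300 micron beads for whom follow-up is available". Bead size is thus a condition of entry.
- **Surefire eligibility.** The only procedural criterion in 3.5.2 is "Patients undergoing Surefire DEB-TACE procedure as clinically determined to be part of their standard of care treatment plan". It names no bead size.
- **Surefire treatment.** Section 3.8 fixes the drug amount ("The Doxorubicin dosing used in the DEB-TACE will be based upon tumor volume as follows") and lists delivery endpoints, but gives no bead size. It adds: "In hypervascular tumors, the additional use of bland spheres may be needed to achieve the DEB-TACE delivery endpoint".
- **Device limit.** The only size bound for the Surefire group is catheter compatibility in 2.2.1: "embolic hydrogel particles 500 μ m or less in size". This describes the device and is not a study condition.
- **Control selection.** The controls are called matched in 2.4.1, 2.4.2 and 3.1 and randomly sampled in 3.3. No matching variable is listed anywhere.
- **Analysis.** In 4.4, LRR is compared by an unadjusted Fisher's exact test. The tumor-size model contains catheter type, age and sex. The Cox models contain treatment group, age, sex and a stage/severity variable. No embolic variable appears in any of them.

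**The concern.** The hypothesis in 2.4.2 attributes a better tumor response to delivery through the Surefire catheter. That reading requires the two groups to be alike in what was delivered. As written, an endhole patient treated with beads outside 100-300 microns is left out of the comparison, while a Surefire patient treated with such beads is kept in. The compatibility limit of 500 microns permits beads above the control range and states no lower bound.

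The protocol itself treats embolic delivery as relevant to outcome. Section 2.1.5 links dense accumulation of spheres in the tumor to better results, and 2.3 lists variable delivery and dosimetry among the problems to be solved. If bead sizes differ between the groups, an embolic effect could pass for a catheter effect or hide one.

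**Working it through.** **Step 1: the rules side by side.**

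| Item | Endhole controls | Surefire patients |
|---|---|---|
| Bead size | 100-300 microns required (2.4.1) | Not set in 3.5.2 or 3.8; device limit of 500 microns (2.2.1) |
| Bland spheres | Not mentioned | Allowed in hypervascular tumors (3.8) |
| Matching on embolic | None listed (3.3) | None listed (3.3) |
| Embolic term in analysis | None (4.4) | None (4.4) |

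The bead-size row is a documented one-sided rule. The bland-sphere row is a statement on one side and silence on the other, so it shows no difference in use.

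**Step 2: the plan's own power figures.** Inputs from 4.3: control LRR 30%, alpha 0.05 (two-sided assumed, since the plan does not say), 100 controls and 50 Surefire patients. Power is the sum, over all pairs of recurrence counts (a, b) for which Fisher's p ≤ 0.05, of Bin(a; 100, 0.30) × Bin(b; 50, p).

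| Surefire LRR (p) | Plan | Exact, usual two-sided p | Exact, doubled one-sided p |
|---|---|---|---|
| 25% | 0.07 | 0.079 | 0.066 |
| 20% | 0.21 | 0.225 | 0.197 |
| 15% | 0.47 | 0.502 | 0.459 |
| 10% | 0.78 | 0.814 | 0.780 |

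The plan's figures reproduce within 2 points under the doubled p-value. Under the usual two-sided p-value the last two rows come out about 3 points higher. The arithmetic of 4.3 is not in dispute. The usual two-sided version is used below.

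**Step 3: what an embolic difference could do (illustration).** If a fraction f of Surefire patients had beads outside the control range, and that alone shifted the outcome by d points, the spurious catheter effect would be f × d. The documents give neither quantity. Assuming f = 20% to 50% and d = 10 to 20 points, the range runs from 0.2 × 10 = 2 points to 0.5 × 20 = 10 points, in either direction.

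Assume next that the catheter has no effect and only the embolic shifts the Surefire LRR away from 30%:

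| Net shift in Surefire LRR | Fisher rejection rate, 100 vs 50 |
|---|---|
| 0 | 4.0% |
| -5 points | 7.9% |
| -10 points | 22.5% |
| +5 points | 8.4% |
| +10 points | 21.2% |

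In the other direction, suppose a true 20-point benefit (30% vs 10%). An adverse embolic shift of 5 points makes this 30% vs 15%, and one of 10 points makes it 30% vs 20%. Power falls from 81% to 50% or 23%.

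**Step 4: what a common condition could cost.** Same test, 30% vs 10%, 100 controls, with only the qualifying Surefire patients kept:

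| Qualifying Surefire patients | Share outside the condition | Exact Fisher power |
|---|---|---|
| 50 | 0% | 0.81 |
| 40 | 20% | 0.73 |
| 25 | 50% | 0.54 |

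**The case against.** The strongest reply is that the documents show an omission, not a difference. Both groups come from one hospital, and treatment is described as standard of care. All Surefire patients may have received 100-300 micron beads, in which case bead size confounds nothing. This stands, and it is why the point says *may be* confounded.

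Three stronger readings are tempting and are not supported:

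- **That bland spheres differ between the groups.** Section 3.8 says "the additional use of bland spheres may be needed to achieve the DEB-TACE delivery endpoint", but nothing says that endhole patients did not receive them.
- **That the protocol's claim to standardise is false.** Section 3.1 says "This protocol standardizes DEB-TACE delivery with the Surefire Precision Infusion System". That concerns delivery within the prospective arm and makes no claim across groups. Nor do 2.4.1 and 3.8 contradict each other: one describes the control pool, and the other is silent on bead size.
- **That the trial cannot answer its question.** The sizes in Step 3 rest wholly on assumed values. The plan calls the study a pilot (4.3), and a footnote to 3.5.2 says the data will be used to develop a framework for comparison.

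It is also fair that bead size is only one of several ways in which historical controls may differ, and that restricting the analysis has a price. Neither removes the one-sided rule, which is specific and can be checked from records.

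**Conclusion.** The concern holds as a gap in the plan. Bead size is a selection condition for controls only, and nothing in the sampling or the analysis compensates. If bead sizes differ, their effect cannot be separated from the catheter's. Whether they differ, by how much and in which direction cannot be known from the documents. The 2 to 10 points and the rejection rates in Step 3 are therefore illustrations, not estimates of bias.

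The power figures assume a two-sided alpha of 0.05, a 30% control LRR, 100 controls, and every counted patient evaluable for recurrence. The case report form and Instructions for Use are not shown, so whether bead size was recorded, or limited further, cannot be judged. The point should be addressed before any catheter comparison is reported.

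**What to change.** 1. **Tabulate** bead size and bland-sphere use by group from the procedure records, as part of the baseline comparison in 4.4.
2. **Apply the same 100-300 micron condition to both groups** in the catheter comparison, and report the all-Surefire result alongside it.
3. **State the resulting sample size and power.** If every Surefire patient meets the condition, the bead-size concern closes with no loss. If not, the loss follows Step 4.
4. **Report bland-sphere use descriptively or as an adjustment.** Do not use it to exclude patients from the main comparison. It depends on tumor vascularity and on reaching the delivery endpoint, so exclusion would select on a decision made during the procedure and could remove different tumors from each group.

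The cost is SAP wording and a review of at most 50 prospective procedure records, plus the control records for bland-sphere use. Section 4.6 ended data entry on 18 June 2018, so this extraction would need to be arranged outside the study database, and it presupposes that the records state bead size. These are analysis rules only; no change to treatment is proposed.
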